2.1.2 Human Phase I Safety and Pharmacokinetics

A recent dose escalation study has been performed evaluating 70 healthy adult men and women of non-child bearing potential who were age 18-45 (NCT02234570, DMID 12-0053, unpublished). Seven dose groups were studied (0.5, 1, 3, 7.5, 15, 30 and 60 mg/kg) and each dose group was comprised of 10 subjects of whom eight received study drug and two received placebo. All subjects received a single dose of study drug or placebo and were followed for 14 days for safety and the pharmacokinetics of oxfendazole and metabolites including fenbendazole and oxfendazole sulfone were evaluated in blood and urine. There were no study drug associated serious adverse events identified. Sixteen unsolicited adverse events were experienced by 10 subjects. Six were considered related to the study treatment. Five of the events were mild and included one subject with an increased PR interval 14 days following the dose of study drug, and the remaining events were gastrointestinal events (nausea, loose stools, intestinal gas, and diarrhea, all of which occurred in the 30 or 60 mg/kg dose groups. There was one event, a sore throat that was considered moderate in intensity. Mild to moderate laboratory events were seen in hematology and chemistry tests. There were no patterns identified related to timing of the abnormal laboratory studies or dose of oxfendazole and the placebo group had similar rates of abnormal laboratory values.

The median time of maximum concentration (T_{max}) occurred at 2 hours and the geometric mean maximum concentration (C_{max}) ranged from 943.9-6768.4 ng/mL. The exposure was non-linear, plateauing at 15 mg/kg. The half-life ($t_{1/2}$) was consistent between groups and ranged from 8.5-11 hours. The overall fraction of drug excreted in the urine was very low and the geometric mean AUC_{0-t} for the sulfone metabolite was 11.5-15% of oxfendazole AUC_{0-t} while fenbendazole AUC_{0-t} was less than 1% of oxfendazole AUC_{0-t} for each dose group.

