Subjects will be administered oxfendazole by a study nurse or investigator on days 1, 2, 3, 4 and 5. Subjects will be fasting (water is permitted) for eight hours prior to, and for two hours after, the administration of drug. On the 1st and 5th day of drug administration intensive blood sampling will be performed for PK studies (pre-dose and 30 minutes, 1, 2, 3, 4, 6, 9, and 12 hours following the dose). On days 2, 3 and 4, blood sampling for PK studies will be performed prior to each dose and 2 hours after each dose. On day 6, blood sampling for PK studies will be performed approximately 24 hours following the dose on day 5. Monitoring will start immediately after dosing and will continue for 10 days. Safety laboratories will be performed on days 1, 3, 5, 8 and 10. EKG studies will be performed at screening, two hours after doses on days 1, 3 and 5, and day 8. Subjects will be interviewed to monitor for AEs and SAEs. Blood sampling for PK studies will be performed on days 8 and 10. In addition, prior to study drug administration on days 2-5, if subjects self-report any new signs or symptoms a targeted physical exam may be performed, if indicated, and the new signs or symptoms will be recorded as an AE or SAE as appropriate.

Following blood sampling performed on each day of dosing, subjects will be allowed to return home. Subjects will be counseled to avoid drug, alcohol and tobacco use through the end of the study (Day 10 for groups 1-3 and Day 14 for group 4).

In the food effects evaluation, 12 subjects will be enrolled into the single dose cross over group. Group 4 can be enrolled concurrently with groups 1, 2, and 3. In group 4, half of the subjects will receive a single dose of 3 mg/kg of oxfendazole following an 8 hour fast and the other half will receive a single dose following a high fat meal. Each subject will be followed with safety laboratories, EKGs and PK studies for 7 days at which time they will cross over to receive a single dose of oxfendazole (3mg/kg) following either a high fat meal or following an 8 hour fast.

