- Counseling on avoidance of pregnancy.

7.2 Enrollment/Baseline - GROUPS 1, 2 and 3

Clinic Visit 01, Day 1

Eligible subjects will be asked to return to the Clinical Research Unit (CRU) having fasted for 8 or more hours.

General.

- Review inclusion/exclusion criteria (including assessment of time of last oral food intake and laboratory results obtained at the screening visit, Day 00).
- Absence of medications in the past 48 hours will be confirmed.
- A brief interim medical history will be taken.
- A routine physical examination that assesses general appearance and the following areas/systems, including skin, lymph nodes, HEENT, neck, respiratory, cardiovascular, pulmonary, abdomen, extremities, musculoskeletal, and neurological will be performed by a clinician licensed to make diagnoses.
- Vital signs including oral temperature, blood pressure, and pulse will be obtained.
- Perform a urine pregnancy test for female subjects of childbearing potential.
- A heparin lock will be inserted, blood will be drawn (10 mL) for baseline PK (prior to product administration), and (15 mL) for safety labs (hemoglobin, white blood cell count, including neutrophil count, platelet count, INR, partial thromboplastin time, creatinine, Na, K, CL, CO₂, blood urea nitrogen, ALT, AST, and total bilirubin.
- Collect urine for dipstick testing for protein and glucose
- Enter subject into electronic data entry system.

Administration of Study Medication

A study nurse will administer a single oral dose of oxfendazole to the subject. Escalating dose levels of 3, 7.5 and 15 mg/kg will be evaluated sequentially.

- Subjects will remain fasting (water is permitted) for two hours after the administration of drug.
- Lunch and dinner will be provided. Subjects will be allowed to eat snacks but will be asked to avoid drinking grapefruit juice and excessive (>2 cups) coffee.
- 10 mL of blood for oxfendazole level will be drawn predose and at 30 minutes, 1, 2, 3, 4, 6, 9, and 12 hours (all times have a window of +/- 15 minutes except the 9 and 12 hour samples which have a window of +/- 30 minutes- it is critical to record the exact time of blood draw).
- Obtain EKG 2 hr after study drug administration (+/- 20 minutes)
- Assess AEs and SAEs throughout the day and prior to discharge from the CRU.
- Counsel on need to avoid alcohol, drugs, tobacco and medications throughout the study.
- Counseling on avoidance of pregnancy.

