- Lunch and dinner will be provided. Subjects will be allowed to eat snacks but will be asked to avoid drinking grapefruit juice and excessive (>2 cups) coffee.
- 10 mL of blood for oxfendazole level will be drawn predose and at 30 minutes, 1, 2, 3, 4, 6, 9, and 12 hours (all times have a window of +/- 15 minutes except the 9 and 12 hour samples which have a window of +/- 30 minutes- it is critical to record the exact time of blood draw).
- Obtain EKG 2 hr after study drug administration (+/- 20 minutes)
- Assess AEs and SAEs throughout the day and prior to discharge from the CRU.
- Counsel on need to avoid alcohol, drugs, tobacco and medications throughout the study.
- Counseling on avoidance of pregnancy.
- Ask subject to remain fasting (water is permitted) for 8 hours prior to returning to the clinic in the morning.

Clinic Visit 06, Day 6

- Vital signs including oral temperature, blood pressure, and pulse will be obtained.
- A targeted physical exam will be performed if indicated
- Review concomitant medications
- Review for AEs and SAEs.
- Counsel on need to avoid alcohol, drugs, tobacco and medications throughout the study.
- Collect 10 mL of blood for oxfendazole level approximately 24 hours after dosing on day 5 (+6 hours)

Clinic Visit 07, Day 8 (+/- 1 day)

- Vital signs including oral temperature, blood pressure, and pulse will be obtained.
- A targeted physical exam may be performed, if indicated.
- Review concomitant medications
- Review for AEs and SAEs.
- Counsel on need to avoid alcohol, drugs, tobacco and medications throughout the study.
- Collect 10 mL of blood for oxfendazole level
- Collect 15 mL of blood for safety panels (hemoglobin, white blood cell count, including neutrophil count, platelet count, INR, partial thromboplastin time, Na, K, Cl, CO₂, blood urea nitrogen, creatinine, ALT, AST, and total bilirubin).

-
- Collect urine for dipstick testing for protein and glucose.
 - An EKG will be performed and will be reviewed by a cardiologist.

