- Perform a urine pregnancy test for females of childbearing potential.
- A targeted physical exam may be performed, if indicated.
- Review concomitant medications
- Review for AEs and SAEs
- A heparin lock will be inserted, blood will be drawn (10 mL) for baseline PK (prior to product administration)

Administration of Study Medication

A study nurse will administer a single 3 mg/kg oral dose of oxfendazole to the subject.

- For subjects who fasted during the first day of study drug administration, provide high fat breakfast prior to study drug administration. Approximately 30 minutes (+/- 15 minutes) following completion of the meal, the study nurse will administer a single 3 mg/kg oral dose of oxfendazole.
- For subjects who received a meal prior to the first day of study drug administration, subjects should fast for 8 hours prior to receipt of study drug and remain fasting (water is permitted) for two hours after the administration of drug.
- Lunch and dinner will be provided. Subjects will be allowed to eat snacks but will be asked to avoid drinking grapefruit juice and excessive (>2 cups) coffee.
- 10 mL of blood for oxfendazole level will be drawn at 30 minutes, 1, 2, 3, 4, 6, 9, and 12 hours (all times have a window of +/- 15 minutes except the 9 and 12 hour samples which have a window of +/- 30 minutes- it is critical to record the exact time of blood draw).
- Perform EKG approximately 2 hours following study drug (+/- 20 minutes)
- Assess AEs and SAEs throughout the day and prior to discharge from the CRU.
- Counsel on need to avoid alcohol, drugs, tobacco and medications throughout the study.
- Counseling on avoidance of pregnancy.

Clinic Visit 05, Day 9: (or 1 day following second dose)

- Vital signs including oral temperature, blood pressure, and pulse will be obtained.
- A targeted physical exam may be performed, if indicated.
- Review concomitant medications
- Review for AEs and SAEs

-
- Draw 10 mL of blood for oxfendazole level -approximately 24 hours after dosing on day 8 (+/- 2 hours)
 - Counsel on need to avoid alcohol, drugs, tobacco and medications throughout the study.

7.7 Final Study Visit 06 Day 14 (+/- 2 days) - GROUP 4

- Vital signs including oral temperature, blood pressure, and pulse will be obtained.
- A targeted physical exam may be performed, if indicated.
- Review concomitant medications
- Review for AEs and SAEs
- Draw 10 mL of blood for oxfendazole level

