8 STUDY PROCEDURES/EVALUATIONS

8.1 Clinical Evaluations

Medical History: Will be obtained by interview of the subjects. Subjects will be queried regarding a history of significant medical disorders of the head, eyes, ears, nose, throat, mouth, cardiovascular system, lungs, gastrointestinal tract, liver, pancreas, kidney, nervous system, blood, lymph glands, endocrine system, musculoskeletal system, skin, and genital/reproductive tract. A history of any allergies, cancer, immunodeficiency, psychiatric illness, substance abuse, and autoimmune disease will be solicited.

Interim Medical History: Will be obtained by interview of the subjects. Subjects will be queried regarding new signs or symptoms that have occurred since the screening medical history was obtained.

Concomitant Medications: All current medications and medications taken in the 30 days before the screening visit (prescription and over-the-counter drugs) will be documented, as well as vitamins and supplements, and alternative/complementary medications through the last study visit. Assessment of eligibility also will include a review of prohibited medications (per the exclusion criteria).

Physical Examination: This examination will be conducted at Screening and Visit 1 and will assess general appearance including height and weight (at Screening only), vital signs (blood pressure, temperature, pulse), and the following areas/symptoms: skin, lymph nodes, head, eyes, ears, nose, throat, respiratory, cardiovascular, abdomen, extremities, musculoskeletal, and neurological.

Vital Signs and Targeted Physical Examination: Vital signs will be collected at each scheduled study visit and at the Early Termination Visit. Vital signs will be collected if indicated at the unscheduled visit. A targeted physical examination may be conducted at any study visit based on interim medical history.

Adverse Events Assessments: Subjects will be asked if they have any new symptoms since the prior visit. Please see section 9.2.1 and 9.2.2.

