11.4.3 Analysis of Safety

Adverse experiences (spontaneous reports) will be coded into MedDRA® preferred terms. The number of subjects experiencing unsolicited adverse events and the number of spontaneous events, classified using MedDRA® System Organ Classes and Preferred Terms, reported throughout the study after treatment administration will be tabulated by cohort. The severity and relationship to study product of the unsolicited adverse events will also be assessed. Serious adverse events will be described. A complete listing of adverse experiences for each subject will provide details including severity, relationship to treatment, onset, duration, and outcome. Solicited clinical laboratory results and vital signs will be graded and summarized by cohort and study day.

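### No blood-pressure or temperature reading is specified between a dose and about 20 hours after it, so the vital-sign summary cannot show a silent, short-lived change near peak concentration

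*Protocol*

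**What the plan says.** **Groups 1-3.** In Protocol 7.2 (Day 1) the vital-sign item, "Vital signs including oral temperature, blood pressure, and pulse will be obtained", is in the general list, before the study-medication block. In 7.3 (Days 2-5) it opens each visit, ahead of the pre-dose PK draw and the dose. The items listed after dosing are PK draws, the EKG on Days 1, 3 and 5, and adverse-event assessment through the day on Days 1 and 5. Vital signs are not among them. Later readings are on Days 6, 8 and 10. The Day 6 visit is tied to the last dose by its PK draw: "Collect 10 mL of blood for oxfendazole level approximately 24 hours after dosing on day 5 (+6 hours").

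**Group 4.** Sections 7.5 and 7.6 follow the same order on Days 1 and 8, with later readings on Days 2, 4, 9 and 14. What is timed close to the dose is the EKG: "Perform EKG approximately 2 hours following study drug (+/- 20 minutes").

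**Frequency and analysis.** Section 8.1 sets the frequency per visit: "Vital signs will be collected at each scheduled study visit and at the Early Termination Visit". Appendix A has one mark per visit and no clock time. Section 4 says "Monitoring will start immediately after dosing and will continue for 10 days", but no vital-sign procedure follows from that sentence. Section 11.4.3 says "Solicited clinical laboratory results and vital signs will be graded and summarized by cohort and study day", and Appendix B supplies grades for fever, hypertension and hypotension. The SAP covers PK only and adds nothing on this point.

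**The concern.** Safety is the primary objective, and vital signs are graded outcomes. A related Grade 3 adverse event, or two of Grade 2, counts in the sentinel and dose-escalation criteria of 9.5.1 and 9.5.2. If readings are taken where the procedures place them, the Day 1 row of the vital-sign table is a pre-drug value. The rows for Days 2-5 are then trough values for the previous day's dose, and no row describes the hours around Cmax.

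A table with no graded abnormality could be taken as evidence against an acute effect on blood pressure or temperature. The schedule cannot supply that evidence for a change that causes no symptoms and has passed by the next visit. This bears most on two exposures that the study is meant to characterise: the fifth daily dose, and the dose after a high-fat meal.

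**Working it through.** The plan states no figure on this point, so there is none to reproduce. The check has three parts.

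**1. Position of each reading relative to the last dose** (7.2-7.7 and Appendix A, nominal times)

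| Group | Dosing-day reading | Other readings, hours after the most recent dose |
|---|---|---|
| 1-3 | Days 1-5, listed before the dose; on Days 2-5 this is about 24 h after the previous dose | Day 6: 24; Day 8: 72; Day 10: 120 |
| 4 | Days 1 and 8, listed before the dose | Day 2: 24; Day 4: 72; Day 9: 24; Day 14: 144 |

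Vital signs have no window of their own. If they are taken with the PK draw, the earliest reading after a dose is on Day 2, where the draw is 24 h ± 4 h, so 20 h. SAP 2.3 writes the Day 6 window as ± 6 h where Protocol 7.3 has + 6 h. The SAP wording would move the earliest reading to 18 h and leave the conclusion unchanged.

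**2. Concentration left at those times**

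Inputs are from the earlier single-dose study described in Protocol 2.1.2: the median Tmax "occurred at 2 hours and the geometric mean maximum concentration" ranged by dose group, and the half-life "was consistent between groups and ranged from 8.5-11 hours". Assuming mono-exponential decline from the peak, the share of peak left at time t is

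2^(−(t − 2)/t½)

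| t (h) | t½ = 8.5 h | t½ = 11 h |
|---|---|---|
| 18 | 27% | 36% |
| 20 | 23% | 32% |
| 24 | 2^(−22/8.5) = 17% | 2^(−22/11) = 25% |
| 72 | 0.3% | 1.2% |
| 120 | 0.007% | 0.06% |
| 144 | 0.001% | 0.01% |

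**3. Doses affected**

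- Planned doses: 5 × 24 + 2 × 12 = 144. None has a specified blood-pressure or temperature reading later on the dosing day.
- Doses with a 2-hour EKG: 3 × 24 (Days 1, 3, 5) + 2 × 12 (Days 1, 8) = 96.
- Doses without one: 144 − 96 = 48, which are Days 2 and 4 in Groups 1-3 (2 × 24). Protocol 7.3 and SAP 2.3 schedule a 2-hour PK draw on those days.

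**The case against.** **Timing is inferred.** No clock time is given for vital signs, and the lists are not strictly chronological. For example, the pre-dose PK draw also appears inside the study-medication block. A reader might infer that the protocol restricts vital signs to before the dose. It does not say so, and it does not forbid a later reading. The supportable statement is that no post-dose reading is specified. The before-dose position is still the natural reading, and Section 4 places the Day 1 vital signs with the pre-drug review and baseline bloods.

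**Other surveillance exists.** A reader might infer that only an effect lasting about a day could be found. That goes too far. On Days 1 and 5 (Group 4: Days 1 and 8) adverse events are assessed through the day, and 8.1 allows a targeted examination at any visit. A symptomatic change could be caught. The 12-lead EKG at 2 hours shows heart rate, so tachycardia and bradycardia are not part of the gap on EKG days. What remains is asymptomatic change in blood pressure or temperature.

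**Prior data are reassuring.** Section 2.1.1.4 reports no vital-sign change in dogs at single doses up to 100 mg/kg. Sections 2.1.2 and 2.3.1 describe no blood-pressure or fever event in people at single doses up to 60 mg/kg, four times the highest single dose here, with exposure plateauing at 15 mg/kg. The target organs named in 2.3.1 are marrow and liver, which the safety laboratories cover. This lowers the expected risk. It does not replace a reading under repeated dosing or after food, and the documents do not say when vital signs were taken in the earlier human study.

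**Day 1 is already called baseline.** Section 7.2 and Appendix A label that visit so. This stands, and only a label in the 11.4.3 summary is missing.

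**Conclusion.** The concern holds in this limited form. No scheduled blood-pressure or temperature reading is specified between dosing and about 20 hours after any of the 144 planned doses. The first reading after a dose comes when about 17-25% of peak remains at the nominal 24 hours (23-32% at 20 hours). Others fall as late as 6 days after a dose. The summary in 11.4.3 cannot show an asymptomatic, transient change in either measure near Cmax.

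This rests on three assumptions: that procedures are done in the order listed, that decline from the peak is mono-exponential, and that the single-dose Tmax and half-life carry over. The documents give no fed Tmax, so the fed peak may not be at 2 hours.

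A reader might go further and infer that post-dose safety is unmonitored, or that the halting rules cannot operate. The documents do not support that. EKG, laboratory and adverse-event surveillance continue, and none of the study halting criteria in 9.5.3 is a blood-pressure or temperature threshold. This is a cheap improvement to the safety data, and no reason to doubt the design as a whole.

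**What to change.** 1. In Protocol 7.2, 7.3, 7.5, 7.6 and Appendix A, state the time of vital signs relative to dose.
2. Add blood pressure and temperature, with pulse optional, at the existing 2-hour EKG/PK contact on Days 1, 3 and 5 in Groups 1-3 and on Days 1 and 8 in Group 4. This covers 96 of the 144 planned doses. The 2-hour PK draw on Days 2 and 4 could carry the same reading for the other 48. If it is not used, say that those doses are left out by choice.
3. In 11.4.3, label the pre-dose Day 1 value as baseline and summarise post-dose values separately from pre-dose and trough values. Add a note that the documents give no fed Tmax, so the 2-hour fed reading may not coincide with the peak.

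The cost is a few minutes of nurse time and one CRF field per reading, plus a line in Appendix A. No extra visit or blood draw is needed, because the subject is already present at 2 hours.

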2.1.1.4 Animal Safety

The potential cardiovascular or toxicity effects of oxfendazole (OXF) were investigated after drug administration to beagle dogs (14). Following administration of single oral doses of oxfendazole at 0, 5, 25 or 100 mg/kg, no changes in body weight, body temperature, clinical laboratory evaluations (hematology, serum chemistry, and coagulation studies), changes in vital signs (blood pressure, heart rate) or changes in electrocardiogram evaluations were noted.

A two week toxicology study of oxfendazole administered orally to rats at doses from 0-200 mg/kg, was recently performed (15). There were no changes in feeding, behavior or physiological measurements (15). Animals in the highest dose groups were euthanized on day 8 because of severe toxicity and mortality. Females had a higher incidence of mortality and more severe adverse effects than did males administered the same dose; correspondingly higher OXF exposure was found in females than in males. At the higher doses, WBC depletion was dose related, being severe in females at the highest dose. WBC recovered when OXF administration was suspended. Target organs of toxicity were bone marrow, epididymis, liver, spleen, testis and thymus. Hepatic midzonal fatty change was present in male and female rats administered the higher doses; these changes were still present after a 14-day recovery period. However, no effects on liver enzymes were seen in the clinical chemistry results, suggesting that these effects did not result in overt hepatotoxicity or compromised hepatic function; therefore, the toxicologic significance of this observation is unclear.

Several toxicology studies were performed at the time of Synanthic® approval. In single dose toxicology studies in mice, rats and dogs. One rat that received a dose of 6400 mg/kg, orally died from enteropathy. In subchronic toxicology studies in which rats and dogs were dosed over a two week period at doses ranging from 11-200 mg/kg, orally, decreases in neutrophil count, hemoglobin and hematocrit were seen at the higher doses, as were pathological changes in the liver (with hepatocyte vacuolation), gastroenteropathy, testes, bone marrow, liver, spleen, and thymus. Toxicology studies demonstrated mild hepatotoxicity in rats fed 2.1 or 7 mg/kg

daily for a year (16). Similar dog studies showed no toxicity (16). Fetotoxicity was noted in rats and mice (16).

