14.7 Future Use of Stored Specimens

No specimens will be saved for future use. Once the study has been completed DMID will instruct the site and Fisher BioServices to destroy all residual samples. The destruction of residual samples will be appropriately documented.

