Bilirubin (serum total) mg/dL	1.3 – 2.0	2.1 – 2.5	> 2.5
Bilirubin – when ALT \geq 105 (Hy's law)	1.3 -1.5	1.6 – 2.0	> 2.0
Amylase- U/L	200-270	271-360	>360
Lipase- U/L	176-270	271-360	>360
Hemoglobin (Female) – g/dL	11.0 – 11.5	9.5 – 10.9	< 9.5
Hemoglobin (Male) – g/dL	12.0 – 12.5	10.0 – 11.9	<10.0
WBC Increase – cell/mm ³	11,001 – 15,000	15,001 – 20,000	> 20,000

WBC Decrease – cell/mm ³	2,500 – 3,500	1,500 – 2,499	< 1500
Lymphocytes Decrease – cell/mm ³	750 – 1,000	500 – 749	< 500
Neutrophils Decrease – cell/mm ³	1,500 – 2,000	1,000 – 1,499	< 1000
Eosinophils – cell/mm ³	500-750	751-1500	> 1500
Platelets Decreased – cell/mm ³	120,000 – 130,000	100,000 – 119,999	<100,000
INR –(International Normalized Ratio of the prothrombin time)	1.3 to <1.7	1.8- <2.3	≥ 2.4
PTT – seconds (partial thromboplastin time)	>ULN-42.1	42.2– 50.0	> 50.0
Fibrinogen increase – mg/dL	>ULN – 500	501 – 600	> 600
Fibrinogen decrease – mg/dL	<LLN – 140	125 – 139	<125
Urine *	Grade 1	Grade 2	Grade 3
Protein	1+	2+	>2+
Glucose	1+	2+	>2+
Blood (microscopic) – red blood cells per high power field (rbc/hpf)	5-10	11-50	> 50 and/or gross blood

* The laboratory values provided in the tables serve as guidelines and are dependent upon institutional normal parameters.

* Institutional normal reference ranges should be provided to demonstrate that they are appropriate.

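### Groups 1-3 give 345 mL of blood over Days 1-10, 270 mL of it in 10 mL PK draws, enough to produce some Grade 1 hemoglobin events with no drug effect; cut the draw to what the assay needs

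*Protocol*

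**What the plan says.** **Sampling.** For Days 1 and 5, Protocol 7.2 and 7.3 state: "10 mL of blood for oxfendazole level will be drawn predose and at 30 minutes, 1, 2, 3, 4, 6, 9, and 12 hours". For the days between, section 4 states: "On days 2, 3 and 4, blood sampling for PK studies will be performed prior to each dose and 2 hours after each dose". Day 6 adds one sample (7.3): "Collect 10 mL of blood for oxfendazole level approximately 24 hours after dosing on day 5". Two later ones follow (section 4): "Blood sampling for PK studies will be performed on days 8 and 10". Section 4 also sets the safety panels: "Safety laboratories will be performed on days 1, 3, 5, 8 and 10". Sections 7.2-7.4 give each panel as 15 mL. SAP 2.3 implies the same number of PK draws. The Appendix A footnote for Days 3 and 4 differs: it lists only the predose sample.

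**Grading.** Section 5.1 requires hemoglobin within the normal range, which Appendix D gives as 11.9-15.5 g/dL for women and 13.2-17.7 for men. The limits in Appendix B are absolute. The row "Hemoglobin (Female) – g/dL" puts Grade 1 at 11.0-11.5, Grade 2 at 9.5-10.9 and Grade 3 below 9.5. For men the grades are 12.0-12.5, 10.0-11.9 and below 10.0.

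**Drug signal.** Section 2.1.1.4 reports from two-week rat and dog studies: "decreases in neutrophil count, hemoglobin and hematocrit were seen at the higher doses". Section 2.3.1 names bone marrow as a principal target organ at higher animal doses.

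**Use of the blood.** Protocol 8.2.2 and SAP 2.4 describe an assay of oxfendazole only. Section 14.7 states: "No specimens will be saved for future use".

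The text available for review states no cumulative blood volume, though the consent pages are not part of it. Neither the grading, nor the halting rules, nor the analysis allows for blood loss.

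**The concern.** Repeated sampling lowers hemoglobin by dilution as plasma volume refills. A woman may enter at 11.9 g/dL, which is 0.4 above Grade 1 and 1.0 above Grade 2, so a fall of moderate size can produce a graded laboratory event without any drug effect. Such events are AEs under 9.2.1 and 9.2.3. Groups 1-3 are open label without placebo, so nothing concurrent shows how much of a fall comes from sampling.

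Hemoglobin also fell in the animal studies. The clinician who must call a mild fall related or not related therefore has two live explanations. The error can go either way: a sampling effect may be charged to the drug, or an early marrow effect may be put down to blood loss. Each escalation decision rests on one group of eight, before the next dose level has been given.

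**Working it through.** **1. Volume (Groups 1-3).** The Day 1 predose sample appears twice in 7.2 and is counted once. The 15 mL taken at screening is left out.

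| Day | PK draws | PK mL | Safety mL | Lost before this visit, mL |
|---|---|---|---|---|
| 1 | 9 | 90 | 15 | 0 |
| 2 | 2 | 20 | 0 | 105 |
| 3 | 2 | 20 | 15 | 125 |
| 4 | 2 | 20 | 0 | 160 |
| 5 | 9 | 90 | 15 | 180 |
| 6 | 1 | 10 | 0 | 285 |
| 8 | 1 | 10 | 15 | 295 |
| 10 | 1 | 10 | 15 | 320 |
| Total | 27 | 270 | 75 | 345 after Day 10 |

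Read literally, the Appendix A footnote removes two 10 mL samples: 345 - 20 = 325 mL. The last hemoglobin can reflect only what was drawn before it, so 320 mL is the relevant loss on Day 10.

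**2. Fall in hemoglobin.** Assumptions not in the documents: blood volume BV, full plasma refill and no red-cell replacement. With volume lost V and baseline Hb0:

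- progressive dilution: fall = Hb0 × (1 - exp(-V/BV))
- linear approximation: fall = Hb0 × V/BV

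For V = 0.320 L:

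- BV 6.0 L, Hb0 11.9: 0.62 (linear 0.63) g/dL
- BV 3.5 L, Hb0 15.0: 1.31 (linear 1.37) g/dL
- BV 4.5-5.5 L, Hb0 11.9-15.0: 0.67-1.07 g/dL over both formulas

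Individual cases, assuming 65 mL/kg for women and 70 mL/kg for men:

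- 60 kg woman at 13.2: 13.2 × (1 - exp(-320/3900)) = 1.04 g/dL
- 80 kg man at 14.5: 14.5 × (1 - exp(-320/5600)) = 0.81 g/dL
- 50 kg woman at 11.9: 11.9 × exp(-320/3250) = 10.8 g/dL, which is Grade 2

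**3. Distance to each grade from the lowest eligible baseline.**

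- Women: 11.9 - 11.5 = 0.4 to Grade 1; 11.9 - 10.9 = 1.0 to Grade 2; more than 2.4 to Grade 3.
- Men: 13.2 - 12.5 = 0.7; 13.2 - 11.9 = 1.3; more than 3.2.

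**4. Share of women graded on Day 8 or Day 10.** This is a simulation. Assumptions: hemoglobin mean 13.4, SD 0.9, truncated to 11.9-15.5; weight mean 68, SD 12 kg (floor 45); 65 mL/kg; within-subject CV 2.5-3%; results rounded to 0.1 g/dL. Each range runs over the CV.

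| Scenario | Grade 1 or more | Grade 2 |
|---|---|---|
| No sampling | about 1% or less | almost 0 |
| 10 mL draws, no red-cell recovery | 16-18% | 2-3% |
| 10 mL draws, 30% recovery | about 8-10% | about 0.5-1% |
| 10 mL draws, 50% recovery | 5-6% | well under 1% |
| 4 mL draws, no recovery | 5-6% | well under 1% |

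**5. Chance of two Grade 2 women in one cohort,** before any relatedness filter. With p = 0.02-0.03, 1 - (1-p)^n - n·p·(1-p)^(n-1) gives 0.2-0.5% for n = 4 women and 1.0-2.2% for n = 8. If two results from the same woman also count, the model gives 0.3-0.6% per woman. That adds at most 4 × 0.6% = 2.4% with four women, or 8 × 0.6% = 4.8% with eight.

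**The case against.** The case against has several sound parts.

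- **Primary endpoint.** A reader might infer that every graded fall enters it. It does not: section 3.2.1 counts AEs related to oxfendazole, and 9.2.1 has a clinician judge each one. Sampling enters only by misattribution.
- **Halting.** A reader might infer a real risk of a false stop. Every Grade 3 limb requires relatedness and a fall far beyond anything sampling can cause. The Grade 2 limb needs two results, with the small chances in step 5. The Grade 2 bullet in 9.5.2 omits the relatedness condition that section 4 and 9.5.1 carry. Those passages must be reconciled, but that is a separate point.
- **Separability.** A reader might infer that marrow toxicity could not be recognised. That goes too far. Sampling is identical in Groups 1-3, so a trend over dose is not confounded. Neutrophils, WBC and platelets are measured on the same days. Group 4 loses (21 × 10) + (3 × 15) = 255 mL with only two doses, an imperfect but usable comparison. The human single-dose study (2.1.2) found no laboratory pattern by dose.
- **Size.** No red-cell replacement is the extreme case, and the population inputs are assumed.
- **Purpose.** A reader might infer that the volume serves nothing. Section 8.2.2 gives its use, a PK assay, and reserve plasma for repeats is legitimate even if residues are later destroyed. The documents simply do not say why 10 mL is needed.

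These points limit the consequence. They do not remove the blood loss or its effect on Grade 1 events.

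**Conclusion.** The point holds as a modest, avoidable bias. The 345 mL total, and the 295 and 320 mL lost before the Day 8 and Day 10 hemoglobins, follow from the visit schedule (325 mL in total on the literal Appendix A footnote). The resulting fall of about 0.6-1.4 g/dL by Day 10 depends on an assumed blood volume of 3.5-6.0 L, full refill and no red-cell recovery; recovery makes it smaller. On the stated assumptions 16-18% of women would be graded from sampling alone, or 5-10% with 30-50% recovery.

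The effect is on Grade 1, occasionally Grade 2, hemoglobin events and on the relatedness call within each uncontrolled group. The documents do not support a claim that the dose comparison is biased, that Grade 3 could result, or that halting is likely.

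**What to change.** In Protocol 7.2-7.7, 8.2.2 and Appendix A, and in SAP 2.3-2.4, reduce the PK draw to the volume the validated single-analyte assay needs, including repeat assays, once the laboratory has confirmed that figure. The documents do not give it, so 4 mL is only an illustration:

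- Groups 1-3 total: 27 × 4 + 75 = 183 mL instead of 345 mL
- Lost before Day 8: 25 × 4 + 45 = 145 mL instead of 295 mL
- Group 4 total: 21 × 4 + 45 = 129 mL instead of 255 mL

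Reconcile the Appendix A footnote for Days 3 and 4 with section 4, section 7.3 and SAP 2.3 in the same edit. Section 11.4.3 already summarizes laboratory results by cohort and study day, so a further table would add little.

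The cost is smaller tubes, a change to the laboratory instructions and less reserve plasma for re-assay. No time point is lost.
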